The following relates to Section 2.2.2 secondary objective (iii) Status of indication-related characteristics (alteration of diagnosis, stroke (CHADS2/ CHA2DS2-VASc) and bleeding risk score (HAS BLED) if available) will be summarised, plus pattern of anticoagulant treatment adherence at the end of the 12 week observation period (as estimated from Medication Possession Ratio††††††) will be summarised. The frequency and reasons for attendance to clinics for review and management of anticoagulation and/or acute hospitalisations (including hospital referrals) will also be summarised, where reported. Alterations in treatment programme (change in dose, other drugs) will be described, as will any reason(s) for stopping treatment (including switching) and transition plans to other anticoagulants.

Changes in these indication-related characteristics and treatment details will be examined by comparing values at index and at 12 weeks post index date. Exploratory analysis may include data mining and descriptive measures for describing alterations in treatment programme.

The number of pregnancies, trimester of first exposure and details of births, terminations and miscarriages will be presented. The number of deaths (as recorded in medical charts) in the total cohort for each month of exposure will be calculated. Causes of death will also be described by system-organ class.

Sensitivity analyses will examine any under-reporting using data provided from the patients GP.

Where no. days held will be calculated from information derived from 12 week questionnaire on number of prescriptions and average treatment length of prescriptions (usually given in 7, 14,28,56 day repeats); no. days supply expected will assume chronic use from start to end of study observation or treatment stop date (if stopped)

4.7.5 To quantify the incidence risk and rate of events reported in the 12 week observation period in both the rivaroxaban and contextual cohort and in patient subgroups of special interest.

The following relates to Section 2.2.2 secondary objectives (i) and (iv) regarding a) major bleeding outcomes as specified in the primary objective for the contextual cohort, b) other major or non-major clinically relevant bleeding outcomes not specified in the primary objectives, c) thromboembolism (recurrent and incident) and d) any other events reported in the 12 week observation period.

For major bleeding events not specified in the primary outcome, each of the individual components of the major bleeding criteria ( a fall in haemoglobin of 2 g/dL or more, or a transfusion of 2 or more units of packed red blood cells or whole blood, or a fatal outcome - as per table 2) will be summarised. Where an individual has one or more criterion for an individual organ site of interest, this will also be summarised – in such individuals the first report will be regarded as the incident event.

For clinically relevant non-major bleeding events, each of the individual associated components (as per table 2 such as requiring medical intervention, unscheduled contact (visit or telephone call) with a physician, (temporary) cessation of study drug treatment, or associated with discomfort for the subject such as pain or impairment of activities of daily life) will be summarised. Where an individual has one or more criterion for a clinically relevant non-major bleeding event, this will also be summarised – in such individuals the first event report will be regarded as the incident event.

Analysis of event data for purposes of signal detection includes exploring overall risk and rate for the observation period and time to onset profiles. The methodology provides a numerator (the number of reports of an event) and a denominator (person-time at risk), both collected within a known time frame. This allows for the calculation of crude risks (percent of total valid cohort exposed) and rates (Incidence Densities-ID; person-time incidence rates) for each event separately. Each event may be reported in response to a closed question (for example information on each individual major and/or clinically relevant non-major bleeding risk component), or as free text in response to open questions on the data collection forms. Such analyses will be performed using 'Higher-level' event terms from the MedDRA dictionary where possible. The risk profile of the overall cohorts and sub-group of interest

(based on index date characteristics, including whether anticoagulant naïve, rivaroxaban naïve or past (other anticoagulant user) will be described by presenting summary tabulations (by rank) of counts and incidence risk of reported events, and crude event rates (IDs).

Calculating and ranking crude ID rates is one of a number of standard quantitative evaluations used in event monitoring methodology for signal generation purposes as part of initial inspection of all event data for general safety surveillance. It is used as a means of alerting early potential signals as priorities for further evaluation. Medical judgment however is also part of this evaluation and prioritization process. Crude Incidence Densities (ID) ‡‡‡‡‡‡ can be calculated by week in order to quantify rates of events. IDs will be calculated, for each given time period (t), for all events reported in patients who continue to take rivaroxaban for a given time period, or for whom the date of stopping is known. Only the first report of an event in an individual patient is used in the calculation of IDs. They are usually expressed as the number of first reports of an event per 1000 patient-weeks. This assumes the pattern of use is continuous. The numerator will be the first reports of events reported as occurring after the index date and during treatment.§§§§§§§ For this study, IDs will be calculated for each event for each week as follows:

$ID_t =$	Number of first reports of an event during treatment for period t x 1000					
	Number of patient-weeks of treatment for period t					
Thus,	$ID_t =$	Nt x 1000				
		Dt				
where:	$N_t =$	Number of first reports of an event during treatment for period t,				
and	$D_t =$	Number of patient-days of treatment for period t / 7				

IDs will also be calculated for each event for all 12 weeks during treatment combined (IDA), and the first week after stopping (IDSW1) if patient stopped (and where patients are recorded as remaining on treatment for at least 1 week) after index date.

<sup>‡‡‡‡‡‡‡ It should be noted such quantification of rate does not only reflect the rate attributable to the drug but also reflects the background rate in the general population and rate attributable to other factors such as age or other disease risk factors

<sup>§§§§§§§ Ideally, the exposure time would be censored at the time of the first event. However, since there are a large number of health outcomes of interest and the censoring would be different for each outcome, the denominator for the crude ID will not initially include censoring. If an elevated crude ID is identified in this monitoring analysis, a subsequent analysis with appropriately censored denominator will be performed for that outcome.

Sensitivity analyses will examine any under-reporting by including events of interest recorded in primary care medical charts and confirmed on follow-up for those patients discharged to primary care, during the 12 week observation period.

As IDs for the overall cohort may sometimes mask significant signals in specific risk groups, the subgroups defined by specific characteristics (e.g. previous history of VTE or haemorrhage, previous/concurrent use of selected medications, off-label indication groups, rivaroxaban naïve or past user) will have IDs calculated and compared according to strata for relevant events, where appropriate.

It is possible to explore the time taken for an event of interest using parametric time to event models (e.g. Weibull) as described previously, thus providing an additional tool for signal generation purposes. This approach will be explored for events of interest, where counts  $\geq 5$ . If undertaken, a sensitivity analysis will be performed to include in the numerator events reported within 7 days of stopping, and extend the denominator by 7 days

4.7.6 To characterise differences in prevalence of prognostic factors and clinical risk factors for haemorrhage associated with rivaroxaban in comparison with contextual cohort as reported during the first 12 weeks after starting treatment in routine secondary care hospital setting in UK.

This relates to Section 2.2.1 secondary objective (v), the aim of which is to explore the effect of important predictors (prognostics characteristics, selected relevant risk factors and oral anticoagulant on the primary outcomes of interest (haemorrhage), **only if sufficient numbers of cases of primary outcome are reported**. The effect of physician anticoagulant prescribing preference factors (type of novel anticoagulants prescribed in previous calendar month; proportion of novel anticoagulant use of all anticoagulants prescribed in previous calendar month), medical education, setting and institution will be explored as a suitable conditioning (instrumental) variable for modelling..[40] Since, data are likely to be hierarchical the application of a multilevel model for discrete response data will be considered. Odds ratios and 95% confidence intervals will be calculated.

4.7.7 To describe clinical features and management of cases of overdose, major bleeding, VTE events indicating failure of anticoagulation and management of homeostasis in patients undertaking surgery (elective or urgent) reported in the first 12 weeks after treatment initiation in the cohort exposed to rivaroxaban.

The following relates to Section 2.2.3 exploratory objective (ii) . A qualitative assessment of these cases will include evaluation of patient demographic characteristics, treatment details, the detection and clinical features and management of events of interest, resolution, relevant investigations prior to and during therapy, the patient's relevant medical history and concurrent medication and any sequelae. Data will be derived from the SCEM and follow up questionnaires sent to gather other relevant essential information for construction of a case-series summary descriptive table.

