Period of observation for analyses will commence from index date (i.e. actual start date of anticoagulant treatment, not the date first seen by the specialist) and continue for 12 weeks (or less if patient discontinues to be under the care of the specialist HCP; to be established via the 12 week end of observation questionnaire) in order to allow for detection of outcomes associated with oral anticoagulant treatment initiation as recorded in medical charts. This study will also collect information on exposure to any other medicines (including those given as part of acute care management within the four calendar weeks prior to index date) as recorded in medical charts in order to explore impact of those treatments on outcomes of interest. Since patient care is likely to be shared between secondary and primary care for most patients during the 12 week observation period, the patient's GP will be contacted††† to complete a simple questionnaire to collect any information on outcomes of interest that have been recorded in the patient's medical charts held in primary care during the 12 week observation period to minimise under-reporting on selected outcomes. Where additional outcomes are identified that have not be reported by the initiating prescriber, these will be followed-up with the GP to ascertain further information.

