## 4.4.2.3 Patient 12 week end of observation questionnaire

For evaluable patients providing consent and for whom a completed index date questionnaire has been received by the DSRU, after at least 12 weeks of observation, a second questionnaire will be systematically generated to collect clinical information relevant to start of observation and any clinical events of medical interest (including serious adverse event reports [classified using the International Conference on Harmonisation definitions [36]] as recorded in the medical charts during the first 12 weeks of observation.

Data obtained from the 12-week end of observation questionnaire will include:

• Additional information on anticoagulation treatment regimen:

<sup>+++++ Alcohol abuse/excess is classified as intake greater than current recommendation by the NHS guidelines of > 21 units for men or > 14 units for women per week

- details of prior use of oral and parenteral anticoagulant therapy (thienopyridines, aspirin, glycoprotein IIb/IIa inhibitors, heparins)
- If switching anticoagulant to either study drug: details of transition plan (both of prior anticoagulant and either study drug); Reasons for switching.
- Treatment regimen during the 12 weeks observation period (number of prescriptions issued (with dates, posology and duration) if known)
- Dates and reasons for changes in anticoagulant treatment regimen during 12 week observation period‡‡‡‡‡
- All relevant laboratory blood parameters during two-week observation period pre-index date and during 12 week observation where applicable (haemoglobin, platelet count, baseline clotting screen (PT, APTT, Fibrinogen Derived, D-Dimer) [*NB abnormalities would be reported as events*]
- If study drug stopped: date and reason for stopping, details of transition plan to alternative anticoagulant of study drug stopped; if required, details of reversal of anticoagulation therapy and management of bleeding complication.
- Recent ( < 4 weeks prior to index date) and concomitant medications (at index or during treatment):
  - not recommended for concomitant use (including azole antimycotics [e.g. ketoconazole] and HIV protease inhibitors)
  - to be used with caution (including fluconazole, strong CYP3A4 inducers, P-gp inhibitors, non-steroidal anti-inflammatory drugs (NSAIDs), acetylsalicylic acid, oral steroids, hormone and oral contraceptive therapy, platelet aggregation inhibitors or other antithrombotic agents)

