- Misclassification bias will be minimised by well defined outcome and follow-up of medically important events. Patients with selected events of interest will be followedup with regard to co-prescribed medicines and concurrent illness. Events that represent features of the respective indications will be taken into account when signals of potential ADRs to rivaroxaban are investigated (i.e., confounding by indication).
- Time bias may also become an issue if the study collection period, and thus the observation period, is extended because of low prescribing rates.
- Furthermore unidentified poor adherence may also lead to misclassification of exposure. However, as with many observational studies, the degree of patient

compliance in taking the prescribed medication cannot be ascertained. Whilst it is not possible to be sure the patient used the medication, it is almost certain that the patient received it since starting treatment is required for study participation.

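### As worded, the Medication Possession Ratio divides whole prescriptions by a truncated window, so it can exceed 100% and can hide gaps of up to about 27 days

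*Supplement*

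**What the plan says.** Section 4.7.4 (secondary objective iii) summarises the "pattern of anticoagulant treatment adherence at the end of the 12 week observation period", estimated by the Medication Possession Ratio. The footnote, printed after Table 5, defines the two parts.

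- **Numerator:** "no. days held will be calculated from information derived from 12 week questionnaire on number of prescriptions and average treatment length of prescriptions". Prescriptions are described as "usually given in 7, 14,28,56 day repeats".
- **Denominator:** "no. days supply expected will assume chronic use from start to end of study observation or treatment stop date (if stopped".

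The visible text does not limit days held to the same window, cap the ratio, or deal with gaps or leftover supply. It gives no value above which a patient counts as adherent.

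The 12-week questionnaire (section 4.4.2.3) asks for more than the ratio uses: "number of prescriptions issued (with dates, posology and duration) if known", and "If study drug stopped: date and reason for stopping". Section 5.2 carries a general caveat that "unidentified poor adherence may also lead to misclassification of exposure", which does not concern supply that overruns the window.

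**The concern.** The two parts of the ratio cover different periods. The denominator stops at the stop date or week 12. The numerator credits the last prescription in full, even if only one of its days falls inside that window, and it ignores when prescriptions were issued. The result is not the share of the period with drug in hand. It can rise above 100%, and supply left over at the end can offset days earlier on when the patient had none.

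The stake is the adherence description itself. This is the only adherence measure that the plan defines, and it is to be summarised for both cohorts. Two patients with equally complete use can get different values because their prescriptions differ in length. A patient with a gap of several weeks can get the same value as one with none.

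**Working it through.** The documents give no ratio value, cut-off or worked example, so there is no figure of the plan's own to reproduce.

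**Inputs from the documents**
- Prescription length *L* = 7, 14, 28 or 56 days (section 4.7.4 footnote).
- Window: "Period of observation for analyses will commence from index date" and runs for 12 weeks or less (section 4.1). Here that is day 1 to *E* = min(stop date, day 84).
- Days held is read as number of prescriptions *n* × length *L*.

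**Assumption:** the refill and stop days below are illustrative. The documents give no refill timing.

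**Formulas**
- Ratio as worded = *n* × *L* / *E*
- Proportion of days covered = days in 1 to *E* with supply in hand / *E*

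**1. Continuous use to day 84.** Lengths 7, 14 and 28 divide 84 exactly, so the ratio is 84/84 = 100%. For 56-day prescriptions it is 2 × 56/84 = 112/84 = 133.3%. True coverage is 100% in all four cases.

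**2. Stop before supply runs out, no gaps.**

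| Length | Stop day 30 | Stop day 60 |
|---|---|---|
| 7 | 35/30 = 116.7% | 63/60 = 105.0% |
| 14 | 42/30 = 140.0% | 70/60 = 116.7% |
| 28 | 56/30 = 186.7% | 84/60 = 140.0% |
| 56 | 56/30 = 186.7% | 112/60 = 186.7% |

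True coverage is again 100% throughout.

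**3. Late last refill.**

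| Prescriptions | Ratio as worded | Days covered | Longest gap |
|---|---|---|---|
| 56-day, days 1 and 84 | 112/84 = 133.3% | 57/84 = 67.9% | 27 days |
| 28-day, days 1, 29 and 84 | 84/84 = 100% | 57/84 = 67.9% | 27 days |
| 28-day, days 1, 29 and 70 | 84/84 = 100% | 71/84 = 84.5% | 13 days |
| 14-day, last on day 84 | 84/84 = 100% | 71/84 = 84.5% | 13 days |
| 7-day, last on day 84 | 84/84 = 100% | 78/84 = 92.9% | 6 days |

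In the first two rows the patient has supply on days 1 to 56 and on day 84, so 56 + 1 = 57 days are covered and days 57 to 83 are not.

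**4. Gap plus early stop.** For 28-day prescriptions on days 1 and 46 with a stop at day 50, the ratio is 56/50 = 112%. Coverage is (28 + 5)/50 = 66%.

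**5. Gaps that are not hidden.** One 28-day prescription only gives 28/84 = 33.3%. Two with no later refill give 56/84 = 66.7%. In both, the ratio equals the true coverage.

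**6. Effect of a cap at 1.** Continuous 56-day use falls from 133.3% to the correct 100%. The 56-day patient with the 27-day gap also falls to 100%, against 67.9% covered. The 28-day patient with the same gap was already at 100%, so a cap changes nothing.

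**The case against.** The strongest reply is that the equation itself is not in the text available. The footnote starts at the clause explaining its terms, so a cap may stand just before it. Only a protocol is shown, and end-of-window rules for a derived variable often sit in an analysis plan or data management plan. Both points deserve weight, and the first should be checked against the original page. They do not remove the problem. The visible text states how the numerator is built, and step 6 shows that a cap would cure values above 100% without revealing gaps.

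Count and average length may also have been chosen because dates are incomplete. Section 4.4.2.3 asks for them only where known, and the GP form in section 4.4.2.4 lists the primary-care regimen without prescription dates. This stands, and the fix needs a fallback.

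Several stronger readings are tempting, and the documents do not support them.
- A reader might infer that the ratio generally exceeds 100% or depends mainly on pack length. Step 1 shows exactly 100% for three of the four stated lengths.
- A reader might infer that patients with long gaps are classed as adherent. The plan sets no cut-off and classifies nobody, and step 5 shows that some long gaps still score 33% to 67%.
- A reader might object that early stoppers look fully adherent. A gap-free patient who stops at day 30 scores 30/30 = 100% under the fix too. The denominator measures adherence while on treatment, and section 4.7.4 describes stopping separately.
- A reader might infer that the bleeding estimates are affected. The ratio enters none of them: the primary denominator in section 4.7.2 is built from index and stop dates.

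**Conclusion.** The point holds in limited form. As visibly defined, the ratio can exceed 100%: 133% for continuous use of 56-day prescriptions, and 187% for one 56-day prescription stopped at day 30. It can mask up to 27 uncovered days when the last 28- or 56-day prescription is issued at the end of the window. With 14- and 7-day prescriptions the masked gap is at most 13 and 6 days. The direction is certain, because leftover supply can only raise the ratio. How often it happens cannot be estimated, since the documents give no refill timing and the last-refill dates above were chosen to show the limit.

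This rests on reading days held as count times average length, and on no truncation being stated in the missing line. The consequence is confined to the descriptive adherence summary under secondary objective (iii). It is worth correcting because the stated calculation gives wrong values and a better one is available from data already requested.

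**What to change.** Amend the footnote to section 4.7.4 as follows.

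- **Where prescription dates are known:** lay out each prescription from its issue date for its recorded duration. Count the days covered up to min(stop date, day 84), divide by that same window, and report the result as the proportion of days covered. Say how a prescription issued before the previous one has run out is handled.
- **Where dates are missing, including for primary-care prescriptions:** keep the count-based ratio, cap it at 1, and report these patients separately with their number.

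The cost is a change of wording, minor programming, and an adherence table split into dated and undated records. No new questionnaire item is needed, because dates, durations and stop dates are already requested in section 4.4.2.3. How many patients fall into the undated group will depend on how completely those items are filled in.

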# Total number of new cases during 12 week observation period x 100 Population initially at risk

If the observed cumulative incidence from the SCEM study falls within the range expected as set by the precision limits of cumulative incidence from clinical trial data, then the null hypothesis (of no difference) will not be rejected. Cumulative hazard rate methods account for truncation of exposure time and censoring; for these analyses the exposure time would be censored at the time of the first event. Kaplan-Meier plots will be presented to describe timeto event as well as smoothed hazard plots to describe how the baseline risk of an event changes over time. Estimates of the hazard function will also be modelled to determine whether the baseline hazard (risk) of the event increases or decreases with time. A constant hazard over time may be consistent with a background (not caused by the drug) event rate, whereas a non-constant hazard over time may be an indicator of a drug-event relationship. The null hypothesis that the hazard rate of the selected event in patients prescribed rivaroxaban will be constant during the 12 week period following the start of treatment will be tested by fitting a parametric time to event model (e.g. Weibull). Such models have a shape parameter that indicates whether the hazard is significantly increasing or decreasing over time. At least five reports of an event are deemed necessary for modelling purposes.\*\*\*\*\*\*

Several sensitivity analyses will be performed: In one, observation start date will be imputed to be the same as the diagnosis date (i.e the index date will be shifted backwards in time) for those patients for whom a lag period between diagnosis and receiving rivaroxaban treatment was reported. The application of time-varying covariates methodology will enable examination of the impact of any transition from other treatments given as part of initial standard care on the results. In addition, since the primary analysis will be run only to include confirmed cases of incident major bleeding, it will be necessary to explore the reasons for exclusion of incomplete cases and examine their impact on the estimated measure of frequency.

Where possible, data will be stratified according to relevant strong risk factors (e.g. gender, age ( $\leq 60, 60-74, \geq 75$  years), indication and past history of haemorrhage or VTE) and stratum-specific incidence rates examined.

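### Crude incidence densities (section 4.7.5) keep patients in the denominator after their first report, which modestly understates the rates of common events; censoring is applied only on an undefined trigger.

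*Supplement*

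**What the plan says.** In section 4.7.5 the numerator is restricted: "Only the first report of an event in an individual patient is used in the calculation of IDs". The denominator D_t for period t is given as "Number of patient-days of treatment for period t / 7". IDs are to be calculated for each week, for all 12 weeks of treatment combined, and for selected subgroups, where they are compared between strata.

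A footnote to the numerator calls censoring at the first event the ideal. It sets this aside at the first stage because there are many outcomes and each would be censored differently, and makes the second stage conditional: "the denominator for the crude ID will not initially include censoring. If an elevated crude ID is identified in this monitoring analysis", then "a subsequent analysis with appropriately censored denominator will be performed for that outcome". No threshold, reference rate or comparator for *elevated* is given.

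For the primary bleeding outcomes, section 4.7.2 does censor in its hazard analyses: "for these analyses the exposure time would be censored at the time of the first event".

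**The concern.** Numerator and denominator do not describe the same people. After a first report of an event a patient can no longer contribute to N_t for that event, yet the treatment time that follows still counts in D_t. Section 4.7.5 itself describes the denominator as time at risk, and this time is not time at risk of a first report. Each weekly ID is therefore diluted by the share of treated patients already affected, and that share grows over the 12 weeks.

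Three things follow for common or pooled terms, such as composite bleeding or MedDRA higher-level terms:

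- The rate is understated.
- Weekly IDs fall although the hazard is flat. Section 4.7.2 treats a non-constant hazard as a possible sign of a drug effect, so a built-in decline is an unwelcome property in a signal-generation tool.
- Contrasts between strata shrink, because the higher-risk stratum is diluted more.

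The figure that decides whether an outcome gets the censored analysis is the uncensored one, judged by a rule the plan does not state.

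**Working it through.** The plan gives no ID value or bias figure to reproduce, so the size is derived from its definitions.

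**Inputs.** First-report numerator, treatment-time denominator and 12-week period: section 4.7.5. Expected 12-week risks of the primary-site bleeds, 0.4% (DVT/PE) and 0.7% (AF): section 4.2.1. Any bleeding in AF, 28 per 100 patient-years: section 4.8 of the appended product characteristics. Risks of 1%, 5%, 10% and 20% are assumptions chosen to show the range.

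**Model.** Constant hazard λ per week, 12-week risk p, so λ = −ln(1−p)/12. Everyone stays on treatment for 12 weeks, including after an event; this is the worst case.

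- Uncensored 12-week ID = p/12, so uncensored/true = p / (−ln(1−p)).
- Uncensored week-12 ID/true = e^(−11λ) × (1−e^(−λ))/λ.
- Week-12 to week-1 uncensored ID = e^(−11λ) = (1−p)^(11/12).
- Censored at first report: person-time per patient is p/λ, so the ID equals λ overall and in every week.

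**AF any bleeding**, treating the trial rate as a constant first-event hazard: 0.28 × 84/365.25 = 0.06439, so p = 1 − e^(−0.06439) = 0.06236 and λ = 0.06439/12 = 0.005366.

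- 12-week ratio: 0.06236/0.06439 = 0.9685, low by about 3%.
- Week-12 ratio: 0.9427 × 0.9973 = 0.940, low by about 6%.

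| 12-week risk | 12-week ID low by | Week-12 ID low by | Week 12 / week 1 |
|---|---|---|---|
| 0.4% (DVT/PE primary sites) | 0.2% | 0.4% | 0.996 |
| 0.7% (AF primary sites) | 0.35% | 0.7% | 0.994 |
| 1% (assumed) | 0.5% | 0.96% | 0.991 |
| 5% (assumed) | 2.5% | 4.8% | 0.954 |
| 6.2% (AF any bleeding) | 3.2% | 6.0% | 0.943 |
| 10% (assumed) | 5.1% | 9.6% | 0.908 |
| 20% (assumed) | 10.4% | 19.3% | 0.815 |

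**Stopping at the event.** D_t counts treatment time only. If half of affected patients stop treatment at the event, the bias roughly halves. At 6.2%, censored person-time is 0.06236/0.005366 = 11.62 weeks per patient. Adding back half of the remaining 0.38 gives 11.81, and 0.06236/11.81/0.005366 = 0.984, low by 1.6%. If all stop, the bias is zero.

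**Strata.** At assumed risks of 10% and 5%, the uncensored ratio is 0.10/0.05 = 2.00 and the censored ratio is ln(0.90)/ln(0.95) = 2.05.

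**The case against.** The plan discloses the simplification, calls censoring the ideal, and promises it for flagged outcomes. It uses crude IDs for initial screening alongside medical judgement. The bias is also small beside sampling error: if all 1,700 patients bled at the AF rate there would be about 1,700 × 0.0624 = 106 first reports, a Poisson relative standard error of 1/√106, about 10%, against a bias of 3%. In week 12 there would be about 1,700 × 0.005366 × 0.940 = 8.6 reports, a relative standard error of about 34%, against 6%. All of this stands and keeps the point minor. It does not justify the rule, because the bias is systematic and its removal needs nothing that is not already collected.

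A reader might infer more than the documents support:

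- *The ranking of events is distorted.* Under a constant hazard and full follow-up, p/12 and −ln(1−p)/12 both rise with p, so the order is unchanged. The commonest events carry the most bias but also sit highest, and so are the likeliest to be flagged, though without a threshold this is not assured.
- *The ranked table mixes censored and uncensored rates.* The plan tabulates crude rates and calls the censored run a subsequent analysis. It does not say that one replaces the other.
- *A flat hazard will show an early peak.* The artefact is a smooth, mild decline.
- *Weekly IDs are the plan's time-to-onset analysis.* The signal-detection analysis "includes exploring overall risk and rate for the observation period and time to onset profiles", listing rates and onset profiles as separate items. The onset tool named in section 4.7.5 is a parametric time-to-event model as in section 4.7.2, where exposure is censored. That model is optional and needs at least five reports, so it does not replace correct IDs.

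**Conclusion.** The point holds as a minor one. As written, crude IDs in section 4.7.5 are biased low and decline over the weeks under a constant hazard, and the remedy hangs on an undefined trigger. The bias is under 1% for 12-week risks up to 1%. It is about 3% overall and 6% in week 12 at the one common-event rate taken from the documents. It reaches about 5% and 10% overall at assumed risks of 10% and 20%. Contrasts between strata are slightly attenuated.

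These figures assume a constant hazard and continued treatment after the event; stopping at the event makes them smaller. The documents give no event with a 12-week risk of 20%: the label's 22.7% for any bleeding in the DVT trials comes from treatment of up to 21 months. The primary-outcome hazard analyses are censored and are not affected.

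**What to change.** In section 4.7.5, define D_t separately for every event as patient-days of treatment up to the earliest of the first report of that event, the stop of treatment, or the end of the 12-week period, divided by 7. Use this for the weekly and the combined 12-week on-treatment IDs and in all strata. Delete the footnote's trigger, so that no definition of *elevated* is needed for this purpose.

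The cost is one reworded footnote and a few lines of code. Placing a first report in a given week already requires its date, so no new data are needed. The IDs would then agree with section 4.7.2 and with the ideal the plan states.
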